#### **4.5.3.2. Vital Signs**

Summary tables for vital signs will be produced:

- Change from baseline in vital signs (temperature, systolic and diastolic blood pressure, pulse, and respiratory rate) over time
- Frequency and percentage of vital signs results (relative to Normal Range) post-baseline relative to baseline
- Note: values of PCI will be flagged in listings only.

#### 4.5.3.3. ECG

Summary tables for ECG data will be produced:

- ECG findings
- Change from baseline in ECG values
- Maximum QTc values post-baseline relative to baseline by category
- Maximum increase in QTc values post-baseline relative to baseline by category
- Note: values of PCI will be flagged in listings only.

#### 4.6. Other Analyses

##### 4.6.1. Subgroup analyses

Microbiological outcome and response for each visit and treatment group will be also summarized based on the following subgroups for the Micro-MPP analysis set:

- Menopausal age groups: Pre-menopausal age vs post-menopausal age
  - Categories are considered pre-menopausal age: “potentially able to bear children” and “sterile of child-bearing age”. Categories for post-menopausal age: “post-menopausal”
- Frequency of recurrence of UTI in past 12 months: < 3 UTIs in past 12 months vs  $\geq 3$  UTI in past 12 months.
- Frequency of recurrence of UTI in past 24 months: < 5 UTIs in past 24 months vs  $\geq 5$  UTI in past 24 months.
- Baseline *E. coli*:  $\geq 10^4$  to  $< 10^5$  vs baseline *E. coli*  $\geq 10^5$ 
  - If participants have multiple qualifying baseline *E. coli* the participant will be presented under the ‘higher’ of the multiple subgroups
- Baseline eGFR:  $\geq 60$  to  $< 90$  vs eGFR  $\geq 90$

If the number of participants is too small (less than 10%) within a subgroup, then the subgroup categories may be redefined.

CCI

CCI

CCI

## 4.8. Changes to Protocol Defined Analyses

Changes from the originally planned statistical analysis specified in the protocol are detailed in [Table 2](#)

**Table 2 Changes to Protocol Defined Analysis Plan**

SAP version	Protocol Defined Analysis	SAP Defined Analysis	Rationale for Changes
Original	
 
 Microbiological Success:  Microbiological response of <math><10^3</math> CFU/mL for all qualifying E. coli identified at Baseline in urine microbiology count at ToC visit, without receiving other systemic antimicrobials (rescue medications) prior to ToC.   If the Baseline urine microbiology count has <math>>1</math> E. coli strain present at <math>>10^4</math> CFU/mL, both strains must have a response of <math><10^3</math> CFU/mL to achieve microbiological success. 
 
 Microbiological Failure: All other outcomes (for example but not limited to <math>\geq 10^3</math> CFU/mL for any qualifying E. coli identified at Baseline, use of rescue medication prior to ToC, lost to follow-ups before ToC, missing/unevaluable samples at ToC, etc). 
 
	
 
 Microbiological Success:  Microbiological response of <math><10^3</math> CFU/mL for any E. coli (qualifying or non-qualifying at baseline) at test-of-cure.   Any participant in the Micro-MPP population with E. coli <math><10^3</math> CFU/mL (no E. coli) at TOC. 
 
 Microbiological Failure: All other outcomes (for example, but not limited to, <math>\geq 10^3</math> CFU/mL for any E. coli (qualifying or non-qualifying at baseline), use of rescue medication prior to ToC, lost to follow-ups before ToC, missing/unevaluable samples at ToC).   Any participants in the Micro-MPP population with E. coli <math>\geq 10^3</math> CFU/mL at TOC. 
 
	
 
Clarification to microbiological success/failure criteria based on FDA comment
 

Amendment 1	
 
Protocol amendment 4 updated definition of micro-ITT to require "all planned doses" rather than "at least 1 dose" and rename as Micro-MPP.
 
	
 
Definition of Micro-MITT and CCI: All eligible participants randomly assigned to study intervention who receive at least one dose of study intervention and have a Qualifying baseline E.coli (Micro) CCI
 
	
 
CCI
 

SAP version	Protocol Defined Analysis	SAP Defined Analysis	Rationale for Changes
		respectively CCI from a quantitative bacteriological culture of a pre-treatment clean-catch midstream urine specimen.	
Amendment 3	CCI		
	
 
For primary endpoint estimand: Use of rescue medication will be set to non-responder in the endpoint definition.
 
	
 
Use of rescue medication after last dose of study intervention will be set to non-responder in the endpoint definition.
 
	
 
Wording for primary estimand updated to clarify that rescue medication use for population of interest would only occur following the 5 day dosing period.
 

	
 
For secondary endpoints estimand: Use of rescue medication – While on treatment strategy
 
	
 
Use of rescue medication – Treatment policy strategy
 
	
 
Strategy for handling of ICE for estimand for Secondary endpoint – Safety so that all safety data is presented in summaries.
 

	
 
For secondary endpoints estimand: estimand specified for plasma and urine PK parameters
 
	
 
For secondary endpoints estimand: estimand specified for plasma and urine PK concentrations
 
	
 
Updated to align with protocol defined secondary endpoints
 

CCI

CCI

## **6. SUPPORTING DOCUMENTATION**

### **6.1. Appendix 1 Study Population Analyses**

Unless otherwise specified, the study population analyses will be based on the Screened, Enrolled, Randomised or Safety analysis set.

A summary of the number of participants in each of the participant level analysis sets will (defined in Section 3) be provided.

#### **6.1.1. Participant Disposition**

A summary of the number and percentage of participants who completed the study as well as those who prematurely withdrew from the study will be provided. Reasons for study withdrawal will be summarized.

A participant is considered to have completed the study if all periods of the study up to and including the Follow-up Visit have been completed.

A summary of study intervention status will be provided. This display will show the number and percentage of participants who have completed the scheduled study intervention, or have discontinued study intervention prematurely, as well as primary reasons for discontinuation of study intervention.

Rescreened participants will be summarized under their latest participant number.

#### **6.1.2. Demographic and Baseline Characteristics**

The demographic characteristics including age, gender, ethnicity, height/weight at screening and race will be summarized with descriptive statistics. . Pre/post-menopausal /childbearing potential age groups and Glomerular Filtration Rate (GFR) will also be presented. If the summary of demographics meets the criteria for de-identification, as described in the relevant procedural document, a de-identified version will be produced.

History of previous uUTI infections, baseline disease characteristics including baseline uropathogen recovery rate and clinical symptom score, will be summarized.

Past medical conditions and current medical conditions as of screening will be summarized separately.

#### **6.1.3. Protocol Deviations**

Important protocol deviations will be summarized by treatment.

Protocol deviations will be tracked by the study team throughout the conduct of the study. These protocol deviations will be reviewed to identify those considered as important as follows:

- Data will be reviewed prior to unblinding freezing the database to ensure all important deviations (where possible without knowing the study intervention details) are captured and categorised in the protocol deviations dataset.
- This dataset will be the basis for the summaries of important protocol deviations.

Protocol deviations which result in exclusion from the analysis set will also be summarized.

- Data will be reviewed prior to unblinding and freezing the database to ensure all deviations leading to analysis population exclusions are captured and categorised in the protocol deviations ADaM dataset.

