Blinding	
A procedure in which 1 or more parties to the study are kept unaware of the intervention assignment in order to reduce the risk of biased study outcomes. The level of blinding is maintained throughout the conduct of the study, and only when the data are cleaned to an acceptable level of quality will appropriate personnel be unblinded or when required in case of a SAE.
 
In a double-blind study, the participant, the investigator, and sponsor staff who are involved in the treatment or clinical evaluation of the participants and the review or analysis of data are all unaware of the intervention assignment.
 
Partially-blind is to be used for study designs with different blinding levels between different groups, e.g., double-blinded consistency lots which are open with respect to the control group.

Caregiver	
A “caregiver” is someone who:
 
 
lives in the close surroundings of a participant and has a continuous caring role or
 
has substantial periods of contact with a participant and is engaged in their daily health care (e.g., a relative of the participant, a nurse who helps with daily activities in case of residence in a nursing home).
 
 
In the context of a clinical study, a caregiver could include an individual appointed to oversee and support the participant’s compliance with protocol-specified procedures.

Certified copy	A copy (irrespective of the type of media used) of the original record that has been verified (e.g., by a dated signature or by

Term	Definition
	generation through a validated process) to have the same information, including data that describe the context, content, and structure, as the original.
Challenge agent	A product given to trial participants to produce a physiological response that is necessary before the pharmacological action of the IMP can be assessed.
Child in care	A child who has been placed under the control or protection of an agency, organization, institution or entity by the courts, the government, or a government body, acting in accordance with powers conferred on them by law or regulation. The definition of a child in care can include a child cared for by foster parents or living in a care home or institution, provided that the arrangement falls within the definition above. The definition of a child in care does not include a child who is adopted or has an appointed legal guardian.

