### 1.1.1. Estimand for Primary Endpoint

The primary clinical question of interest is: *What is the microbiological response for GSK3882347 assessed at ToC in participants with acute uUTI caused by E. coli at Baseline who completed the planned course of treatment (5 days) and had no major deviations from protocol that would prevent evaluation of microbiological response (as defined in the protocol deviation rules document). Use of rescue medication after last dose of study intervention will be set to non-responder in the endpoint definition.*

The Primary estimand is described by the following attributes:

- Population: Female participants with acute uUTI with a qualifying baseline *E. coli* (Section 6.4) at baseline who completed the planned course of treatment (5 days) and had no major deviations from protocol that would prevent evaluation of microbiological response
- Treatment condition: GSK3882347 CCI mg given orally CCI for 5 days or Nitrofurantoin 100mg given orally twice daily for 5 days.
- Variable: Microbiological response at ToC visit (see Section 4.2.1)
- Summary measure: Frequency and percentage of participants with microbiological response (responder/non-responder) in GSK3882347 treatment group
- Main intercurrent events anticipated:

- Use of rescue medication prior to ToC visit- Composite strategy
- This intercurrent event is captured through the definitions of microbiological response (see Section 4.2.1). Hence the participants who take rescue medication prior to ToC visit will be considered as non-responders.
- Participants who are lost to follow-up prior to ToC, have a missing/ unevaluable sample at ToC, discontinue study treatment due to any reason (withdrawal of consent/AEs/missed doses) will not be included in the analysis and may be replaced at the discretion of the Sponsor.
- Rationale for estimand:

Use of rescue medication may impact microbiological outcomes and its use implies that the treatment the participant received is not working, therefore, the definition of a successful microbiological response precludes the use of rescue medications. In this small, early phase, proof of mechanism study, interest lies in the treatment effect of participants who completed the planned course of treatment and follow important components of the study protocol to establish proof of mechanism.

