## 2. STATISTICAL HYPOTHESES

No formal statistical hypotheses will be tested in this study.

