### 3. ANALYSIS SETS

Analysis Set	Definition / Criteria	Analyses Evaluated
Screened	All participants who signed the ICF and were screened for eligibility.	
 
Study Population
 

Enrolled	
All participants who passed screening and entered the study
 
Note: screening failures [who never passed screening even if rescreened] and participants screened but never enrolled into the study [Met eligibility but not needed] are excluded from the Enrolled analysis set as they did not enter the study.)
	
 
Study Population
 

Randomized	
All participants in the Enrolled analysis set who were randomly assigned to study intervention in the study.
 
Participants will be analyzed according to the intervention they were randomly assigned to.
	
 
Study Population
 

Safety	
All participants in the Randomized analysis set who receive at least 1 dose of study intervention.
 
Participants will be analyzed according to their actual intervention received.
	
 
Safety
 

Microbiological Modified Per Protocol (Micro-MPP)*	
All participants in the Safety analysis set who: receive all planned doses of study intervention; have a Qualifying baseline E. coli from a quantitative bacteriological culture of a pre-treatment clean-catch midstream urine specimen; have completed a ToC visit; have no major protocol deviations that would prevent evaluation of microbiological response.
 
Participants will be analyzed according to their actual intervention received.
	
 
Efficacy
 

CCI

CCI

Analysis Set	Definition / Criteria	Analyses Evaluated
CCI		
Pharmacokinetic (PK)	
All participants in the Safety analysis set who had at least 1 non-missing PK assessment (Non-quantifiable [NQ] values will be considered as non-missing values).
 
Participants will be analyzed according to their actual intervention received.
	
 
Pharmacokinetic
 

CCI		

\*The algorithm for determining qualifying *E. coli* based on microbiology laboratory quantitative culture results is provided in the [Appendix 4](#)

CCI

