#### 4.4. Exploratory Endpoint(s) Analyses

Efficacy results will be presented on the Micro-MPP analysis set, unless otherwise specified.

CCI

- Clinical resolution response
- Clinical symptom score outcome & response

CCI

A blinded clinical review of concomitant medications will be conducted to determine use of systemic antibacterials.

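### The reviews that feed Micro-MPP membership and the antibacterial call are masked, as far as stated, to treatment only, which does not protect a one-arm responder rate from outcome-aware classification

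*SAP*

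**What the plan says.** **The estimate.** SAP 1.1.1 gives the primary summary measure as "Frequency and percentage of participants with microbiological response (responder/non-responder) in GSK3882347 treatment group". SAP 2 adds "No formal statistical hypotheses will be tested in this study", and Protocol 9.3.1 plans no formal comparison with nitrofurantoin. It calls microbiological response the key endpoint for internal decisions. The Protocol synopsis gives 3:1 allocation and stops randomisation at about 21 evaluable participants on GSK3882347.

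**Who is counted.** Among other conditions, Micro-MPP members must "have no major protocol deviations that would prevent evaluation of microbiological response" (SAP 3). SAP 1.1.1 refers to a separate deviation rules document for what counts. It also leaves women with a missing or unevaluable ToC sample out of the analysis.

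**How the calls are protected.** For deviations that lead to exclusion, SAP 6.1.3 says: "Data will be reviewed prior to unblinding and freezing the database to ensure all deviations leading to analysis population exclusions are captured". For important deviations, the same section asks that the work be done "where possible without knowing the study intervention details". For antibacterials, SAP 4.4 says: "A blinded clinical review of concomitant medications will be conducted to determine use of systemic antibacterials". The Protocol's definition of a double-blind study (Section 10.10) covers the participant, the investigator and sponsor staff. For staff involved in "the review or analysis of data are all unaware of the intervention assignment", the mask is to assignment; outcome is not mentioned.

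**The concern.** In a two-arm comparison, deciding exclusions before unblinding works because the reviewer cannot tell which arm an exclusion favours. Here there is no contrast to protect. If a reviewer knows that a woman failed at ToC, excluding her raises the reported rate if she is on GSK3882347 and leaves it unchanged if she is on nitrofurantoin. It cannot lower it. Treatment need not be known for the direction to be clear.

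Two classifications leave room for this: whether a deviation is major enough to prevent evaluation, and whether a ToC sample is unevaluable. A third, whether a drug was a systemic antibacterial taken before ToC, can turn a culture success into a failure. What is at stake is a proof-of-mechanism rate with a denominator near 21, where each call is visible in the result.

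**Working it through.** **1. The plan's own figures.** The synopsis caps randomisation at 122, or 141 if evaluability is lower than expected. At 3:1, the GSK3882347 arm has 122 × 0.75 = 91.5 or 141 × 0.75 = 105.75 women. Reaching 21 evaluable then implies evaluability of 21/91.5 = 23.0% or 21/105.75 = 19.9%. The evaluability rate itself is not visible, so this shows only that the figures are coherent and that the primary denominator is about 21.

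**2. What treatment masking hides.** Let f_G and f_N be the failure rates on GSK3882347 and nitrofurantoin, and assume the evaluable set keeps the 3:1 ratio. The probability that a failing woman is on GSK3882347 is

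0.75 f_G / (0.75 f_G + 0.25 f_N).

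| f_G | f_N | Probability |
|---|---|---|
| 50% | 50% | 75% |
| 50% | 30% | 83% |
| 50% | 20% | 88% |
| 40% | 20% | 86% |
| 30% | 20% | 82% |

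The failure rates are assumed. The probability falls below 75% only if nitrofurantoin fails more often.

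**3. Effect of excluding failures.** With x successes among n women, excluding k failures changes the rate from x/n to x/(n − k). Assume 24 otherwise qualifying women on GSK3882347 with 10 successes (95% Clopper-Pearson, the SAP 4.2.2 method):

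| Failures excluded | Rate | 95% CI |
|---|---|---|
| 0 | 10/24 = 41.7% | 22.1 to 63.4 |
| 1 | 10/23 = 43.5% | 23.2 to 65.5 |
| 2 | 10/22 = 45.5% | 24.4 to 67.8 |
| 3 | 10/21 = 47.6% | 25.7 to 70.2 |

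Three exclusions add 47.6 − 41.7 = 5.9 points, or about 2 points each.

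**4. Range over other assumed counts.** Starting from 21 and excluding 3 failures:

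- 9/21 = 42.9% becomes 9/18 = 50.0% (+7.1)
- 11/21 = 52.4% becomes 11/18 = 61.1% (+8.7)
- 13/21 = 61.9% becomes 13/18 = 72.2% (+10.3)
- 15/21 = 71.4% becomes 15/18 = 83.3% (+11.9)

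That is roughly 2 to 4 points per exclusion, growing with the success rate.

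**5. Antibacterial call.** This changes the numerator, and only for a woman whose ToC culture is below the failure threshold. One such call moves the rate by 1/21 = 4.8 points (10/21 = 47.6% against 9/21 = 42.9%). Few women are likely to be in this position: Protocol 6.8.3 sends those given antibiotic rescue to an early discontinuation visit and requires no later visits.

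**6. Search for an outcome mask.** Protocol Section 8 withholds laboratory results that could unblind from sites and other blinded personnel, unless rescue is necessary. It does not name cultures, and it does not reach symptom scores, investigator-rated resolution or rescue use. No visible text in either document masks outcome from the people doing the SAP 6.1.3 or 4.4 reviews.

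**The case against.** The other side has good points, and several limit the concern.

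- **Access is inferred from silence.** Cultures go to a central laboratory (Protocol 8.1.2), Section 8 restricts results that could unblind, and Protocol 6.8.3 lets the investigator request the baseline culture, which suggests that cultures are not routinely released. Text directly after the blinding statement in Protocol 6.3 is blacked out. This stands: access to ToC counts is not shown.
- **The review does not itself decide exclusions.** SAP 6.1.3 has it capture and categorise deviations; the rules document is meant to say which prevent evaluation. This also stands. That document is not available here, so the remaining discretion cannot be judged. Nor can the definition of an unevaluable sample, because the ToC part of SAP Appendix 6 is not visible.
- **There are other safeguards.** Response is programmed (SAP 4.2.1), deviations causing exclusion are summarised (SAP 6.1.3), and SAP Table 2 mentions a Micro-MITT set needing one dose and a qualifying *E. coli*. These make selective exclusion easier to detect but do not prevent it.

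Three stronger readings are tempting and not supported:

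- **Replacement as a way to remove failures.** Women who are lost, lack an evaluable ToC sample or stop treatment "will not be included in the analysis and may be replaced at the discretion of the Sponsor". Only their replacement is discretionary, and the replacement's outcome is unknown in advance. A treatment completer with a valid failing culture is not on that list.
- **The team follows outcomes during the study.** The synopsis refers to an observed evaluability rate, but evaluability is defined by baseline *E. coli*, and the stopping rule adds only completion of a ToC visit. No ToC counts are needed.
- **A 14-point swing.** Setting 10/21 (47.6%) against 7/21 (33.3%) joins two opposite scenarios, dropping 3 failures and dropping 3 successes. Selection in one direction gives 5.9 points.

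**Conclusion.** The gap is real but modest. The only mask visible for these reviews is to treatment, and that does not protect a single-arm proportion. The documents show an opportunity for outcome-aware classification of a major deviation or an unevaluable ToC sample. They do not show that reviewers see ToC results or that any bias occurred.

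The size is about 2 points per excluded failure in the main illustration, and 2 to 4 points over the other counts tried. All of these counts are assumed, and neither document says how many exclusions to expect. Three exclusions move the estimate by 5.9 points in the main illustration, well inside an interval running from 25.7% to 70.2%. The study tests no hypothesis. This is a cheap improvement to a decision-making estimate, not a flaw that invalidates it. It would fall away if the rules document or the blacked-out text already masks outcome.

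**What to change.** In SAP 6.1.3 and 4.4:

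1. State that the deviation and antibacterial reviews are done without access to post-baseline culture counts, symptom scores or investigator-rated resolution, as well as treatment. Accept that the medication record may itself reveal rescue, so the antibacterial review cannot be fully masked.
2. Judge whether a ToC sample is evaluable from the laboratory's specimen-quality fields, without the counts.
3. Sign and date the Micro-MPP membership list before ToC culture results are released to the reviewers.
4. List each exclusion with its reason and, once outcomes are released, its outcome.

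If the rules document already contains these steps, a cross-reference is enough. The cost is some SAP wording and one masked data extract. The small downside is that reviewers cannot use outcome data to query a deviation.
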